BUN	Blood urea nitrogen
CK	Creatinine kinase
CL/F	Apparent clearance after extravascular administration
CLSI	Clinical and Laboratory Standards Institute
C _{max}	Maximum observed concentration
CRF	Case report form
CRP	C-reactive protein
DRC	Data Review Committee
ECG	Electrocardiogram
ESR	Erythrocyte sedimentation rate
ITT	Intent-to-Treat
MedDRA	Medical Dictionary for Regulatory Activities
MIC	Minimum inhibitory concentration
mITT	Modified Intent-to-Treat
NCA	Non-compartmental (PK) analysis
PCS	Physical health domain score
PK	Pharmacokinetics
SAE	Serious Adverse Event
SAP	Statistical Analysis Plan
SD	Standard deviation
SGOT	Serum glutamic oxaloacetic transaminase
SGPT	Serum glutamic pyruvic transaminase

SMFA	Short Musculoskeletal Function Assessment
SOC	System organ class
T _{1/2}	Apparent half-life after extravascular administration
TEAE	Treatment-emergent adverse event
T _{max}	Time of the maximal observed concentration
VAS	Visual Analog Scale
VR-12	Veterans Rand 12 Item Health Survey
V _{z/F}	Apparent volume of distribution after extravascular administration
WBC	White blood cells
WHO-DD	World Health Organization Drug Dictionary

1. INTRODUCTION

This Statistical Analysis Plan (SAP) is created based on Protocol MBN-101-201 (Version 5.0, 27 July 2017) and describes in detail the statistical methodology and the statistical Analysis to be conducted for the above-mentioned protocol.

2. STUDY OBJECTIVES

2.1. Primary Objective

The primary objective of this study is:

- To evaluate the safety and tolerability of single escalating doses of locally administered MBN-101 or placebo as adjunct to standard of care antimicrobial and surgical therapy.

2.2. Secondary Objectives

The secondary objectives of this study are as follows:

- To evaluate the clinical activity of single escalating doses of locally administered MBN-101.
- To evaluate the pharmacokinetics of single escalating doses of locally administered MBN-101.

3. STUDY DESIGN

3.1. General Study Design and Plan

This is a randomized, single-blind, placebo-controlled multi-center study to assess the safety and tolerability of escalating doses of MBN-101 applied directly to target structures within infected osteosynthesis sites during revision surgery with or without hardware removal and replacement for patients diagnosed with an apparent fracture site infection or to sites of chronic or acute-on-chronic osteomyelitis of the long bone extremities or residual amputated limbs. Three successive cohorts of 8 patients will be enrolled in this trial. Consecutive patients from each of the study sites will be screened for potential participation as they present to the orthopedic service for clinical care for their infections. Patients meeting all eligibility criteria on screening will be offered participation in the study.

Following baseline evaluation, patients will receive standard of care treatment for their postoperative fracture site infection or osteomyelitis that includes systemic antibacterial treatment per institutional standard of care guidelines and debridement/revision surgery with or without hardware removal and placement/replacement as indicated. A single application of MBN-101 or placebo, applied intraoperatively directly to target structures within infected bone sites, will be performed following the final irrigation and debridement procedure and immediately prior to definitive closure. In cases where original hardware is retained, MBN-101 will be applied to all accessible surfaces of hardware and adjacent bone (target structures). In cases where hardware is placed or replaced, or in cases of two-stage procedures, MBN-101 will be applied to all accessible surfaces of hardware and adjacent

bone (target structures) following implantation of hardware and immediately prior to definitive closure. In cases where hardware is not required, MBN-101 will be applied to affected areas of bone only prior to definitive closure. If wounds are left open, the investigational product will be applied immediately prior to definitive closure. The minimum amount of MBN-101 required to achieve a thin coat of the relevant target structures within the infected bone site will be used.

Patients will be randomized 3:1 (active:control) to three successive doses (0.025, 0.075, or 0.25 mg/mL w:v) of MBN-101 (up to 8 mL, for a dose of up to 0.2, 0.6, or 2.0 mg, respectively) or placebo (diluent). Enrollment to the next dose cohort will not commence until an evaluation by the Data Review Committee (DRC) of all available safety data on all patients through Week 6 of study supports escalation to the next cohort.

PK assessments will be performed predose and at nominal 1, 6, 12, 24, 36, 48 (Day 2), 60, 72 (Day 3), 96 (Day 4), and 336 (Day 14; Week 2) hours after administration of study drug.

Patients will undergo study visits at Hour 48 and Weeks 2, 6 and 12. All patients will be followed for a total of 12 weeks after surgery.

I kg **P**

Twenty-four adult male or female patients meeting protocol-specified eligibility criteria may participate in the study, with the objective of having a total of 6 patients per dose level in the MBN-101-treated group and 6 patients in a pooled placebo-treated group.

I g g

Subjects will be randomized in a 3:1 (active:placebo) ratio up to 24 hours prior to surgery via a central randomization scheme.

I g g

This study is a single blind study; however, knowledge of treatment assignment should remain limited to those directly involved with the patient's surgical procedure and other individuals on a need to know basis. In order to provide unblinding data in an emergency in the absence of an individual privy to treatment assignment, sites will be provided with a numbered unblinding envelope corresponding to each numbered test kit the site is delivered. These envelopes will be securely stored in the pharmacy. The unblinding envelope specifies the treatment group of the kit and should only be opened when absolutely necessary. For treatment of adverse events, it should be assumed that the patient has received study drug, thus avoiding the need to unblind the patient. However, in the event the Investigator determines the randomization assignment information is required to treat the patient for an adverse event, the Medical Monitor should be contacted. If the Medical Monitor cannot be reached, the blind may be broken by opening the envelope. The site should document the unblinding process in the patient's source documents.

I g g **P**

[Table 1](#) presents the schedule of events of the study.

Table 1. Schedule of Events

Procedure	Screening	Baseline/ Day of Surgery		Hour 48- 60	Hour 72	Hour 96	Week 2	Week 6	Week 12, EOT	Early Term / Tx Failure
		Day 1	Day 2	Day 3	Day 4	Day 14 ±4 days	Day 42 ±8 days	Day 84 ±8 days		
Review of eligibility criteria	X	X								
Informed consent	X									
Randomization		X								
Surgery/Administration of the Investigational Product		X								
Medical history	X									
Physical exam	X									
Interval physical exam		X	X				X	X	X	X
Hematology	X		X				X	X	X	X
Serology		X					X	X	X	X
Serum chemistry	X		X				X	X	X	X
Urinalysis	X		X				X	X	X	X
Pregnancy test	X	X							X	X
BisEDT Blood levels ¹		X	X	X	X	X				
12-lead ECG	X	X	X						X	X
Vital signs	X	X	X	X	X	X	X	X	X	X
Patient-reported outcomes ²	X						X	X	X	X
Surgical site signs and symptoms		X	X	X	X	X	X	X	X	X
Surgical site pain score		X	X	X	X	X	X	X	X	X
Microbiology		X	(X) ³			(X)	(X)	(X)	(X)	(X)
Radiographic evaluation		X				X	X	X	X	X
Concomitant medications	X	X	X	X	X	X	X	X	X	X
Adverse events		X	X	X	X	X	X	X	X	X

¹ PK blood samples will be collected pre-dose and at nominal 1, 6, 12, 24, 36, 48 (Day 2), 60, 72 (Day 3), 96 (Day 4) and 336 (Day 14; Week 2) hours after administration of the investigational product

² Patient-reported outcomes include the Veterans Rand 12 Item Health Survey (VR-12) and Short Musculoskeletal Function Assessment (SMFA)

³ Microbiology will be performed at any time that a new surgical intervention is required.

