7. ANALYSIS POPULATIONS

The following analysis datasets will be identified for the purpose of analysis.

pgg **P**

All Screened Subjects will include all subjects who signed informed consent for the study.

pkg **f f** **R b**

Intent-to-Treat (ITT) Population will include all subjects who were randomized in the study. A randomized subject may or may not be treated with the assigned study drug.

pdg

Safety Population will include all subjects who received any amount of study drug (active or placebo). All treated subjects will be included in the safety analysis.

png **P f f a bP**

Modified Intent-to-Treat (mITT) Population will include the ITT subjects who received any amount of study (active or placebo) and have at least one post-treatment assessment. The mITT Population is the primary population for efficacy analysis. Post-treatment assessment includes any post-treatment assessment in any study data collected, for example, lab, vital sign, etc.

png **P**

PK Concentration Population will include all subjects with any measurable bismuth blood concentrations.

ppg **P**

PK Evaluable Population will include all subjects providing sufficient measurable bismuth blood concentrations to facilitate determination of PK parameters.

rg **P**

rgg **P P**

Summary statistics will be presented by treatment group. For continuous variables, the number of observations (n), mean, standard deviation (SD), median, minimum, and maximum will be provided. For categorical variables, the frequency and percentage in each category will be displayed.

For summary statistics, the mean and median will be displayed to one decimal place greater than the original value and the measure of variability (e.g. standard deviation) will be displayed to two decimal places greater than the original value. All Analysis will be performed using SAS® Version 9.3.

All safety and efficacy endpoints will be tabulated with descriptive statistics; data from all placebo subjects (2 per cohort; 6 subjects in total) will be pooled. Data from BisEDT treated subjects will be presented by dose (6 subjects per dose) and combined (a total of 18 subjects). If data permits, differences between the treatment groups and 95% confidence intervals for the difference will be presented.

In the event that a subject received study drug treatment that is not the assigned/randomized

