8.2. Handling of Dropouts/Missing Data

For the efficacy endpoint, proportion of treatment failures, subjects who discontinued from the study or died by week 12 will be considered as treatment failures for the efficacy analysis.

For the missing data of SMFA, in the case of the dysfunction index, unanswered items in a category are replaced by the individual's mean score for that category, as long as more than 50 percent of the items in that category have been answered. If $\leq 50\%$ of the items in that category have been answered, the missing data will not be imputed.

In the cases of missing or incomplete dates (e.g. AE and concomitant medications), the missing component(s) will be assumed as the most conservative value possible. For example, AEs with missing start dates, but with stop dates either overlapping into the treatment period or missing, will be counted as treatment-emergent, taking the worst-case approach. When partial dates are present in the data, both a partial start date and/or a partial stop date will be evaluated to determine whether it can be conclusively established that the AE started prior to the start of study drug or ended prior to the start of study drug. If the above cannot be conclusively established based on the partial and/or present dates, then the AE will be considered as treatment-emergent. Actual data values as they appear in the original case report forms (CRFs) will be presented in the data listings.

Missing values for other variables will not be imputed and only observed values will be used in data Analysis and summaries.

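### Efficacy is analysed only in dosed subjects, dosing is settled after randomisation by people who may know the arm, and no planned treatment-failure analysis includes undosed subjects (minor)

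*SAP*

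**What the plan says.** **Order of events (SAP section 3).** On allocation: "Subjects will be randomized in a 3:1 (active:placebo) ratio up to 24 hours prior to surgery via a central randomization scheme". Application of product "will be performed following the final irrigation and debridement procedure and immediately prior to definitive closure". For wounds not closed at the first operation: "If wounds are left open, the investigational product will be applied immediately prior to definitive closure". Two-stage procedures are handled in the same way.

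**Who may know the arm (SAP section 3, blinding paragraph).** The study is single-blind, and "knowledge of treatment assignment should remain limited to those directly involved with the patient's surgical procedure", plus others who need to know. The arrangements for emergency unblinding are meant for use "in the absence of an individual privy to treatment assignment", which presumes that such a person normally exists.

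**Analysis sets (SAP section 7).** The ITT definition allows for randomised subjects who are never treated. The mITT set "will include the ITT subjects who received any amount of study (active or placebo) and have at least one post-treatment assessment". Any post-treatment data item counts as an assessment; a laboratory value or a vital sign is enough.

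**Use of the sets.** Section 8.9 bases all efficacy analysis on mITT. Section 8.1 groups subjects by the treatment they actually received. The one sensitivity analysis for treatment failure (8.9.1) regroups them by assigned treatment, but still within mITT. The only stated use of ITT is the disposition summary in 8.4.

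**Failure rule (SAP section 8.2).** For the proportion of treatment failures, "subjects who discontinued from the study or died by week 12 will be considered as treatment failures for the efficacy analysis".

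**The concern.** A dosed-only efficacy set does little harm when the decision to dose is made blind to the arm. This SAP cannot rely on that argument. Allocation precedes the operation, dosing comes at its end or at a later closure, and the people in control of that step are the ones allowed to know the arm. Entry to the efficacy set is thus a post-randomisation event that could depend on allocation.

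Two gaps follow. First, the SAP plans to present differences in treatment failure between each dose and placebo, with 95% intervals, if data permit. No planned version of that comparison includes the undosed subjects. Second, 8.2 does not say whether its rule reaches a subject who withdraws or dies between randomisation and dosing. As worded it is not limited to dosed subjects, yet such a subject is outside the set on which 8.9 bases the analysis.

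What is at stake is a biased estimate of a secondary, descriptive comparison. There is no hypothesis test, so type I error is not in question, and the primary safety analysis of treated subjects is not affected.

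**Working it through.** **Plan's own figures.** The SAP gives no figure for this point. Its only precision statements (section 4) concern adverse events in dosed subjects, and they reproduce closely: 1 − (1 − 0.385)^6 = 0.946 against the stated 95%, and 1 − 0.05^(1/18) = 0.1533 against the stated 0.153. Neither bears on the choice of efficacy set.

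**Inputs.**
- Group sizes: 6 per dose, 18 active in total, 6 pooled placebo (section 8.1).
- Number of randomised subjects left out of mITT, d: not given. Assumed range 0 to 2 per group.
- Number of failures among those kept, f: not given. Shown over its range.
- No replacement of undosed subjects is assumed. A replacement rule, if there is one, would be in the protocol.

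**Formulae.** The rate in mITT is f/(n − d). The rate in all randomised subjects, with those left out counted as failures, is (f + d)/n. The difference between the two is the effect of the exclusion.

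**Group of 6, one subject left out (d = 1).**

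| f | mITT | All randomised, excluded = failure | Difference (points) |
|---|---|---|---|
| 0 | 0/5 = 0% | 1/6 = 16.7% | 16.7 |
| 1 | 1/5 = 20.0% | 2/6 = 33.3% | 13.3 |
| 2 | 2/5 = 40.0% | 3/6 = 50.0% | 10.0 |
| 3 | 3/5 = 60.0% | 4/6 = 66.7% | 6.7 |
| 4 | 4/5 = 80.0% | 5/6 = 83.3% | 3.3 |
| 5 | 5/5 = 100% | 6/6 = 100% | 0 |

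**Two left out (d = 2).** 0/4 (0%) against 2/6 (33.3%); 1/4 (25.0%) against 3/6 (50.0%); 2/4 (50.0%) against 4/6 (66.7%). Over all f the difference runs from 0 to 33.3 points.

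**Combined active group.** With one of 18 left out and f = 3: 3/17 (17.6%) against 4/18 (22.2%), or 4.6 points.

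**Effect on a comparison.** Suppose a dose group and placebo would each have 2/6 failures, a true difference of 0. If one failing subject leaves the dose group before dosing, the mITT difference is 1/5 − 2/6 = −13.3 points.

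**If d = 0**, the two rates are identical and the issue disappears.

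**Which condition matters.** It is almost entirely the dosing condition. A blood sample is due a nominal 1 hour after administration and any data item qualifies, so the assessment condition could remove only a dosed subject who dies or is lost almost at once. Such a subject would be a failure under 8.2 if kept in the set.

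**The case against.** The other side has a good deal to say.

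- **The imbalance would be visible.** A reader might infer that nothing in the plan could reveal selective exclusion. That goes too far. Section 8.4 tabulates treated and untreated subjects by group in the ITT Population and gives the size of each analysis set. What remains is narrower: the table gives the number undosed, not the effect on treatment failure.
- **Open wounds and staged operations are not lost by design.** It is tempting to say that these patients drop out and that they are at the highest risk of failing. Section 3 defers their dosing to definitive closure and does not cancel it, and the SAP says nothing about their relative risk. What stands is that more can happen between allocation and dosing.
- **8.2 does not contradict 7.4.** Its rule applies to the efficacy analysis, which 8.9 confines to mITT. The sections can be read together as counting discontinuations and deaths within mITT only. The SAP does not state that reading, so this is an ambiguity and not a contradiction.
- **Selection by arm is not shown.** The document allows some operating staff to know the arm. Nothing in it indicates that this knowledge alters who is dosed.
- **The shift is small beside the imprecision.** Exact 95% intervals are about 4% to 78% for 2/6 and 0.5% to 72% for 1/5. A 13-point shift would be unlikely to change a conclusion, and a dosed-subject efficacy set is conventional in a 24-patient dose-escalation study. This limits the priority. It does not supply the missing check, which is cheap.

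**Conclusion.** The point holds as a minor one. Allocation precedes dosing, people who can know the arm control the step between, and all efficacy analyses are confined to a set defined by dosing. The disposition table would show how many subjects went undosed in each arm, but no planned analysis shows what that does to treatment failure, and the population for the 8.2 rule is not stated.

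The size is conditional. In a group of 6, leaving out one subject who would count as a failure lowers the reported rate by 0 to 16.7 points; 2/6 (33%) becoming 1/5 (20%) is a representative case. These figures assume no replacement and that the excluded subject would have failed. The number of undosed subjects is unknown, and the effect is nil if all are dosed.

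A reader might also infer that the release of allocation should be moved closer to dosing. The SAP does not support that step: when allocation is released is a matter of trial conduct for the protocol, which is not at hand, and the analysis gap can be closed without it.

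**What to change.** 1. **Section 8.9.1:** add a sensitivity analysis of treatment failure in the ITT population, grouped as randomised, with undosed subjects counted first as failures and then as non-failures. For a group with 1/5 failures in mITT and one undosed subject, the table would show (1 + 1)/6 = 33.3% and 1/6 = 16.7%. The two versions bracket each group's rate. If undosed subjects occur in both arms, they need not bracket the difference, and the text should say so.
2. **Section 7.4:** drop the post-treatment-assessment condition, so that a dosed subject who dies or is lost before any assessment stays in mITT and is counted as a failure under 8.2.
3. **Section 8.2:** state which population the failure rule covers and, in particular, whether it applies to subjects who leave or die between randomisation and dosing.

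**Cost:** one extra table and a few sentences of SAP wording, with no change to trial conduct or data collection. Counting undosed subjects as failures may make the failure rates look slightly less favourable. If every randomised subject is dosed, the new table simply agrees with the existing as-assigned analysis once item 2 is made.

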4. SAMPLE SIZE CONSIDERATIONS

Sample size (24) for this study was chosen empirically for the purpose of the study without any formal statistical hypothesis to be tested.

Six subjects will receive active drug in each dose cohort. With 6 subjects receiving active drug, the probability of observing at least one of 6 subjects in a dose cohort exhibiting an AE of a specific type is 95% if the true background incidence rate for that event-type were approximately 0.385 or greater. Hence, if an AE of a specific type is not observed in the study in a sample size of 6 subjects receiving active study drug at a given dose, one would “rule-out” this AE as having an incidence rate of more than 0.385 with 95% confidence.

Similarly, if a rare event of interest is not reported in the 18 subjects treated with the active study drug, one could conclude that the rate of the event would be 0.153 or less with 95% confidence.

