8.9.10. Subgroup Analysis for Treatment Failure

If data permit, the following selected subgroups may be performed for subgroup analysis of treatment failure.

1. Area of the infected site
2. Method of fracture fixation
3. Type of infection (per identified microorganism)
4. Anatomic location of the surgery site
5. Hardware retention status (retained vs. exchanged)
6. Type of injuries
7. Method of wound closure
8. Osteomyelitis vs. non-osteomyelitis

rg i g

All safety Analysis will be presented using descriptive statistics and the Safety Population. No inferential statistics will be reported.

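### SAP Section 4: the adverse event rate excluded by 0 of 6 events at 95% confidence is 0.393, not 0.385; separately, Sections 8.1 and 8.10 disagree on confidence intervals for safety

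*SAP*

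**What the plan says.** Section 4 states that the total of 24 was chosen empirically, with no hypothesis to be tested. It then describes what that number can show about adverse events, in three statements:

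- **Detection, one dose cohort.** "Six subjects will receive active drug in each dose cohort". The probability of seeing at least one event of a given type "is 95% if the true background incidence rate for that event-type were approximately 0.385 or greater".
- **Rule-out, one dose cohort.** If no such event is seen among the 6, the event is ruled out "as having an incidence rate of more than 0.385 with 95% confidence".
- **Rule-out, all active subjects.** "if a rare event of interest is not reported in the 18 subjects treated with the active study drug", then "one could conclude that the rate of the event would be 0.153 or less with 95% confidence".

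Two later sections bear on confidence intervals for safety. Section 8.1 (General Statistical Considerations) has a paragraph on the tabulation of safety and efficacy endpoints together, which ends: "If data permits, differences between the treatment groups and 95% confidence intervals for the difference will be presented". Section 8.10 (Safety Analysis) makes the safety analysis descriptive and adds: "No inferential statistics will be reported".

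**The concern.** Safety and tolerability are the primary objective. The 0.385 figure is the SAP's only statement of how precisely one dose cohort can speak to that objective. It is given to three decimals at a stated confidence level, so it should reproduce from the exact binomial calculation, and it does not. The error makes a clean cohort of 6 look slightly more informative than it is.

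The second matter is separate. A programmer building the adverse event tables finds one section that allows confidence intervals for differences and another that excludes inferential output. The SAP does not say which governs.

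**Working it through.** **Inputs (all SAP Section 4).** n = 6 active subjects per dose; n = 18 active subjects in total; confidence 95%; stated limits 0.385 and 0.153.

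**Formula.** With zero events in n subjects, the one-sided 95% exact (Clopper-Pearson) upper limit solves 1 − (1 − p)^n = 0.95, so p = 1 − 0.05^(1/n). The same equation gives the rate at which the chance of at least one event reaches 95%, so it serves both the detection statement and the rule-out statements.

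**Step 1: the 18-subject figure.** 1 − 0.05^(1/18) = 1 − 0.8467 = 0.1533. This matches 0.153 to three decimals and identifies the method used.

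**Step 2: the 6-subject figure by the same method.** 1 − 0.05^(1/6) = 1 − 0.6070 = 0.3930. The SAP has 0.385.

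**Step 3: what 0.385 delivers.** 1 − (1 − 0.385)^6 = 1 − 0.615^6 = 1 − 0.0541 = 0.9459. The confidence is 94.6% and the one-sided error 5.4%, not 5%. For comparison, 0.393 gives 0.94998.

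**Step 4: size of the gap.** 0.3930 − 0.385 = 0.0080, and 0.0080 / 0.3930 = 2.0%.

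**Step 5: could another method explain 0.385?** Limits for 0 of 6:

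| Method | Limit |
|---|---|
| Exact, one-sided 95% | 0.393 |
| Exact, two-sided 95% | 0.459 |
| Wilson, two-sided / one-sided | 0.390 / 0.311 |
| Jeffreys, two-sided / one-sided | 0.330 / 0.264 |
| Uniform prior, one-sided | 0.348 |
| Mid-P, one-sided | 0.319 |
| Agresti-Coull type, two-sided / one-sided | 0.448 / 0.408 |
| Poisson, −ln(0.05)/n | 0.499 |
| Rule of three | 0.500 |

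None gives 0.385. The nearest alternative, two-sided Wilson at 0.390, gives 0.176 for 0 of 18 and so does not fit the SAP's 0.153.

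**Step 6: Sections 8.1 and 8.10 side by side.** The Section 8.1 paragraph opens with safety and efficacy endpoints together and closes with 95% confidence intervals for group differences, if the data permit; nothing in it limits those intervals to efficacy. Section 8.10 rules out inferential statistics for safety. A confidence interval is ordinarily counted as inferential, so on a plain reading the two cannot both govern the safety tables.

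**The case against.** The strongest case for leaving the text alone is that the slip has no consequence. The detection sentence is hedged as approximate, 94.6% rounds to 95%, the sample size was empirical, and no analysis in the SAP uses 0.385. All of this stands, and it is why the correction is minor. The hedge does not reach the rule-out sentence, however, which is an unqualified confidence statement to three decimals beside a companion figure that is right.

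On the second matter, a specific safety section may be read as limiting a general one, and the Section 8.1 intervals are conditional. That is a fair reading, but the SAP does not state it.

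Three stronger readings are tempting, and the SAP does not support them:

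- *A reader might infer that Section 8.10 removes the bounds on which the Section 4 rationale depends.* It does not. A zero-event bound depends only on n and is already printed in Section 4. Event counts will be tabulated by dose, so anyone who sees 0 of 6 or 0 of 18 can apply it. The Section 8.1 intervals are for differences between groups and would not supply that single-group bound in any case.
- *A reader might infer that the correct limits are the two-sided 0.459 and 0.185* (1 − 0.025^(1/6) and 1 − 0.025^(1/18)). The SAP never calls these bounds two-sided. Excluding rates above a limit is naturally a one-sided statement, and 0.153 confirms that this was the calculation used.
- *A reader might infer that counts such as 1 of 6 or 2 of 18 must be given an upper bound.* Section 4 speaks only of events that are not observed, so the SAP breaks no promise by giving none.

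**Conclusion.** The 0.385 figure is wrong. The limit for 0 of 6 at one-sided 95% confidence is 0.393, and 0.385 corresponds to 94.6%. The gap is 0.008 absolute, about 2% relative, and it flatters the precision of a dose cohort. The 0.153 figure for 18 subjects stands. The result assumes independent subjects with a common event rate and exactly 6 treated per dose, which is the setting Section 4 itself uses. Correcting it alters no sample size and no planned analysis, so it is a minor correction.

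The conflict between Sections 8.1 and 8.10 is real and should be resolved, because it decides what the tables for the primary objective contain. It is a separate point and adds nothing to the size of the arithmetic error.

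**What to change.** 1. In Section 4, replace 0.385 with 0.393 in both the detection and the rule-out sentence. Label 0.393 and 0.153 as one-sided 95% upper bounds. Cost: two numbers and a label; the stated precision becomes slightly less favourable.
2. State in the SAP whether safety tables carry confidence intervals. Either limit the interval sentence in Section 8.1 to efficacy endpoints, or reword Section 8.10 to say that no hypothesis tests will be done for safety and that intervals for differences will be descriptive. Cost: one sentence, plus table columns only if the second course is taken.

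Optional: one-sided 95% exact upper bounds on adverse event incidence, by dose and for all 18 active subjects, would extend the Section 4 reasoning to non-zero counts. This is a preference, not a correction.
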